#### **2.4.1.2 Cumulative dose**

Cumulative dose of a study treatment is defined as the total dose given during the study treatment exposure and will be summarized for each of the study treatment components, respectively.

The planned cumulative dose for a study treatment component refers to the total planned dose as per the protocol up to the last date of investigational drug administration. The planned cumulative dose is not summarized/listed. It is used for relative dose intensity calculations.

The actual cumulative dose refers to the total actual dose administered, over the duration for which the subject is on the study treatment as documented in the study treatment eCRF.

For subjects who did not take any drug, the actual cumulative dose is by definition equal to zero for that drug.

For capmatinib (continuous dosing), the actual cumulative dose is the sum of the non-zero doses recorded over the dosing period. The planned cumulative dose is the planned starting dose summed over the same dosing period.

For spartalizumab (intermittent dosing), the actual cumulative dose should be defined based on the days when the subject is assumed to have taken a non-zero dose during dosing periods (number of infusions taken over the treatment period). The planned cumulative dose is the planned starting dose summed over the number of expected infusions during treatment period (e.g, a subject treated for 60 days is expected to have three infusions).

#### 2.4.1.3 Dose intensity and relative dose intensity

For dose intensity calculations, the unit of time for capmatinib will be days and for spartalizumab will be cycles.

For capmatinib, the **dose intensity** (DI) is defined as follows:

DI (mg / days) = Actual Cumulative dose (mg) / Duration of exposure to capmatinib (days).

For example:

The duration of exposure is 56 days and the subject received 50 days of full dosing

DI (mg/day) = 40 000 (mg) / 56 (Day) = 714 (mg/day)

For spartalizumab, the **dose intensity** (DI) is defined as follows:

DI (mg / cycles) = length of cycle \* (Actual Cumulative dose (mg) / duration of exposure to spartalizumab (days)).

For example:

The duration of exposure is 56 days and the subject received two complete infusions

DI (mg/cycle) = 28 (days) \* (800 (mg) / 56 (days)) = 400 (mg/cycle)

For subjects who did not take any drug the DI is by definition equal to zero.

For capmatinib, the **Planned dose intensity** (PDI) is defined as follows:

PDI (mg / days) = Planned Cumulative dose (mg) / Duration of exposure to capmatinib (days)

For example:

The duration of exposure is 56 days, and the subject is planned to receive 56 days of dosing

PDI (mg/day) = 44 800 (mg) / 56 (Day) = 800 (mg/day)

For spartalizumab, the **Planned dose intensity** (PDI) is defined as follows:

PDI (mg / cycles) = length of cycle \* (Planned Cumulative dose (mg) / duration of exposure to spartalizumab (days)).

For example:

The duration of exposure is 56 days, and the subject is planned to receive two infusions

PDI (mg / cycles) = 28 (days) \* (800 (mg) / 56 (days)) = 400 (mg/cycle)

**Relative dose intensity (RDI)** is defined as follows:

RDI = DI (mg / unit of time) / PDI (mg / unit of time)

DI and RDI will be summarized separately for each of the study treatment components, using the duration of exposure of each of the components. RDI will be summarized in percentages. Summary of RDI includes categorical summaries. The RDI categories are < 50%, ≥ 50% - < 75%, ≥ 75% - < 90%, ≥ 90% - < 110% and ≥ 110%.

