## Amendment 1 (13-Oct-2021)

### Amendment rationale

The main purpose of this protocol amendment is to modify the study conduct and data analysis following the sponsor's decision to halt study enrollment on 28-Jul-2021, as communicated to Health Authorities as per local requirements. The enrollment halt decision was based on lack of tolerability observed in capmatinib and spartalizumab combination treatment in the run-in part (Part 1) of the trial.

Immediately following the enrollment halt, below procedural changes have been performed:

- All ongoing subjects were discontinued from spartalizumab treatment and continue to receive single agent capmatinib, given the proven tolerability and efficacy of capmatinib monotherapy in this study indication.
- Enrolled subjects who had not started study treatment were to receive capmatinib single agent treatment from the start

Final | Due to the change in the study treatment following spartalizumab discontinuation, this study can no longer appropriately assess the clinical activity of the combination. Therefore, data collection requirements will be simplified and the study objectives will be updated, as follows:

- The centralized review of study imaging which was put in place to provide blinded and independent efficacy assessment of the combination treatment is no longer required.
- As blinded and independent tumor assessments will no longer be performed, the primary endpoint of the study will be amended to ORR by investigator assessment as per RECIST 1.1, [REDACTED]. The primary endpoint analysis will be based on the estimation of ORR and hypothesis testing of ORR will not be performed.
- PFS and DCR by investigator assessment will be the study secondary endpoints. PFS will be reported using Kaplan Meier analysis. [REDACTED]

The secondary estimand constructed for DOR is no longer applicable.

- In order to capture any potential delayed treatment effect of the combination, BOR and PFS will take into account all available tumor assessments irrespective of spartalizumab discontinuation due to any reason including sponsor decision. The intercurrent events of the primary estimand were updated accordingly.

- [REDACTED]
- [REDACTED]

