## Study Update

As of 28-Jul-2021 when enrollment was halted, 28 patients were treated with capmatinib plus spartalizumab and 3 patients were in screening in the run-in part (Part 1) of the study. The patients who were on combination treatment have discontinued spartalizumab and are continuing on capmatinib single agent since the enrollment halt. The patients who were in screening at the time of the enrollment halt have started receiving capmatinib single agent treatment. As of 06-Sep-2021, 19 patients were still on treatment with capmatinib.

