**Table 1-1 Study objectives**

Objectives	Endpoints
Primary Objectives	Endpoints for primary objectives
To evaluate the anti-tumor activity of capmatinib in combination with spartalizumab	Overall Response Rate (ORR) by investigator assessment as per RECIST 1.1
Secondary Objectives	Endpoints for other secondary objectives

 
To assess safety and tolerability of capmatinib in combination with spartalizumab
 
To further evaluate the anti-tumor activity of capmatinib in combination with spartalizumab
 
To evaluate the PK of capmatinib and spartalizumab
 
	
 
Safety: incidence and severity of AEs and SAEs, changes in laboratory values, vital signs and ECGs. Any clinically significant lab, vital signs, ECG abnormalities will be captured as an AE
 
Tolerability: dose interruptions, reductions, and dose intensity
 
Disease Control Rate (DCR) and PFS by investigator assessment as per RECIST 1.1
 
Concentrations and derived PK parameters of capmatinib and spartalizumab
 

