### 2.1.1.6 On-treatment assessment/event and observation periods

For all safety analyses, the overall observation period will be divided into three mutually exclusive segments:

- ***pre-treatment period***: from day of patient's informed consent to the day before first administration of study treatment
- ***on-treatment period***: from date of first administration of study treatment to 30 days after date of last actual administration of any study treatment (including start and stop date)
- ***post-treatment period***: starting at day 31 after date of last administration of study treatment

If dates are incomplete in a way that clear assignment to pre-, on-, post-treatment period cannot be made, then the respective data will be assigned to the on-treatment period.

Safety summaries will primarily include only data from the on-treatment period. Select summaries of related adverse events and death will be produced for the combined on-treatment and post-treatment periods of study treatment (see [Section 2.8.1](#) and [Section 2.8.2](#)).

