#### **2.4.1.1 Duration of exposure for investigational drug**

Duration of exposure to capmatinib (days) = (last date of exposure to capmatinib) – (date of first administration of capmatinib) + 1.

With:

1. The first date of exposure for capmatinib is the first date when a non-zero capmatinib dose was administered and recorded on the study treatment eCRF.
2. The last date of exposure to capmatinib is the end date from the last dose administration record non-zero capmatinib dose is recorded in the study treatment eCRF.

Duration of exposure to spartalizumab (days) = (last date of exposure to spartalizumab) – (date of first administration of spartalizumab).

With:

1. The first date of exposure for spartalizumab is the first date when a non-zero spartalizumab dose was administered and recorded on the study treatment eCRF.
2. The last date of exposure to spartalizumab is the end date from the last dose administration record non-zero spartalizumab dose is recorded in the study treatment eCRF + 27 days (if no death or no lost to follow-up is observed).
3. The last date of exposure to spartalizumab is the earliest date among last dose administration record non-zero spartalizumab dose + 27 days and date of death if the subject died.
4. The last date of exposure to spartalizumab is the earliest date among last dose administration record non-zero spartalizumab dose + 27 days and date of last contact date if the subject was lost to follow-up.

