#### 2.4.2 Dose reductions, interruptions and permanent discontinuations

The number of subjects who have dose reductions, permanent discontinuations or interruptions, and the reasons, will be summarized separately for each of the study treatment components.

The 'Type of change' field from the study treatment CRF pages will be used to determine the dose interruptions. Dose reductions will be derived programmatically using the dosing information as described below.

The corresponding fields 'Reason for change' will be used to summarize the reasons.

A dose change is recorded when 'Dose change' is entered on the 'Type of change' field on the DAR CRF page, where actual dose administered/total daily dose is different from the prescribed dose. In protocol version 01, dose re-escalation of capmatinib after dose reduction will be allowed only once, given no AE leading to dose modification is observed after at least 1 cycle (4 weeks) of study treatment at the reduced dose. The dose re-escalation will be considered as a dose change. For the purpose of summarizing interruptions and reasons, in case multiple entries for interruption that are entered on consecutive days with different reasons will be counted as separate interruptions. However, if the reason is the same in this mentioned multiple entries on consecutive days, then it will be counted as one interruption.

**Dose reduction** (only for capmatinib): A dose reduction where the prescribed dose level is lower than the previous prescribed dose level or where the actual dose administered/total daily dose is lower than the calculated dose amount based on the prescribed dose. Therefore, any dose change to correct a dosing error will not consider a dose reduction. Only dose change is collected in the CRF, number of reductions will be derived programmatically based on the change and the direction of the change.

**Dose interruption:** Actual dose administered equal to zero, between the first and last non-zero doses, following a non-zero actual dose administered. Number of dose interruptions and corresponding reason will be summarized.

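### Capmatinib dosing and adverse events are pooled across combination time and later capmatinib-alone time, so no planned summary isolates the tolerability of the combination

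*SAP*

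**What the plan says.** SAP Table 1-1 sets the objective as "To assess safety and tolerability of capmatinib in combination with spartalizumab" and gives the endpoint as "Tolerability: dose interruptions, reductions, and dose intensity".

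The protocol's Study Update records what happened to these subjects: "The patients who were on combination treatment have discontinued spartalizumab and are continuing on capmatinib single agent since the enrollment halt". Protocol 9.2.1 sets no fixed end to capmatinib. The study closes when all subjects have stopped and completed follow-up, or when those ongoing transfer to another source of the drug.

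The SAP then works as follows.

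- **Exposure (2.4.1.1):** "The last date of exposure to capmatinib is the end date from the last dose administration record non-zero capmatinib dose". For spartalizumab the last date is the last infusion + 27 days, or death or last contact if earlier.
- **Dose intensity (2.4.1.3):** "DI and RDI will be summarized separately for each of the study treatment components, using the duration of exposure of each of the components".
- **Reductions and interruptions (2.4.2):** summarised by component. An interruption is any zero dose between the first and last non-zero doses. The section also notes that under the amended protocol "dose re-escalation of capmatinib after dose reduction will be allowed only once".
- **Adverse events and laboratory data (2.1.1.6, 2.8.1, 2.8.3):** the on-treatment period runs "from date of first administration of study treatment to 30 days after date of last actual administration of any study treatment".
- **Reporting (2.1, 2.2.3, 4):** there is one arm, the combination. No subgroup is defined and no change to the protocol analyses is declared.

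**The concern.** The sponsor changed the regimen partway through for every subject still on the combination, but the summaries meant to describe the combination carry on across the change. Capmatinib dosing days, dose changes, adverse events and worst laboratory values from the capmatinib-alone period enter the same figures as those from combination time. The dosing rules also changed: Amendment 1 added guidance specific to monotherapy and newly allowed re-escalation.

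This matters because enrollment was halted for lack of tolerability of the combination, and there will be only one clinical study report. A reader of that report would want to know how capmatinib dosing held up, and what toxicity occurred, while the combination was given or could still act. No planned table shows that.

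The treatment-policy strategy for stopping spartalizumab (SAP 1.2.1 and 2.5.3) does not settle the matter. It is defined for best overall response only.

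**Working it through.** **1. The plan's own example.** SAP 2.4.1.3 takes 50 days of full dosing in 56 days of exposure. Dose intensity = 50 × 800 / 56 = 714.3 mg/day (stated: 714). Planned intensity = 800 mg/day. Relative dose intensity (RDI) = 714.3 / 800 = 89.3%, in the 75 to <90% category. The example reproduces.

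**2. The same subject with capmatinib-alone days added.** Assume full dosing after the switch, so RDI = (50 + X) / (56 + X).

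- X = 4: 54/60 = 90.0%, already the next category
- X = 40 (days from the halt to 06-Sep-2021): 90/96 = 93.8%
- X = 168: 218/224 = 97.3%
- X = 365: 415/421 = 98.6%

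**3. The direction is not fixed.** SAP 2.4.1.2 keeps the planned dose at the starting dose, so a subject who stays reduced carries the reduction into the later period. In protocol Table 6-2, 300 mg BID is 75% of 400 mg BID and 200 mg BID is 50%. Assume 3 months of combination at RDI 60%, then 12 months alone:

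- at 95%: (3 × 0.60 + 12 × 0.95) / 15 = 88%
- at 75%: (3 × 0.60 + 12 × 0.75) / 15 = 72%
- at 50%: (3 × 0.60 + 12 × 0.50) / 15 = 52%

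The first moves the subject up from the 50 to <75% category. The second raises the figure within the category. The third lowers it.

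**4. Crude counts.** The number of subjects with at least one adverse event, reduction or interruption cannot fall when time is added. Assume constant weekly hazards of 0.02 on the combination (84 days = 12 weeks) and 0.005 on capmatinib alone. The share with an event is 1 − exp(−0.02 × 12 − 0.005 × X/7):

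- X = 0: 21.3%
- X = 40: 23.6%
- X = 168: 30.2%
- X = 365: 39.4%

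**5. How many subjects.** The Study Update gives 28 treated with the combination, 3 who started on capmatinib alone, and 19 still on capmatinib on 06-Sep-2021. At most 3 of the 19 never had spartalizumab, so at least 19 − 3 = 16 of the 28 had capmatinib-alone time by then.

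**6. A boundary the protocol already uses.** Sections 6.5.2, 10.1.1 and 10.1.3 follow safety to 150 days after the last spartalizumab dose, and Table 8-1b moves thyroid testing to clinical indication at that point. With no infusion after the halt, the window closes by 28-Jul-2021 + 150 days = 25-Dec-2021. Later on-treatment events would still be counted in the combination column.

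**The case against.** The strongest reply is that much of the combination's tolerability is still reported. Spartalizumab dose intensity uses spartalizumab's own exposure, and spartalizumab discontinuations are summarised with reasons. Exposure durations are given for each drug, all doses and adverse events are listed, and the protocol states the reason for the halt. Reporting each component over its whole exposure follows protocol 12.3 and 12.5.2.3. The summaries are descriptive, with no test or threshold attached.

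This stands, and it limits the point. A reader might infer that the report could not address the safety objective or document why enrollment stopped. The documents do not support that: what is missing is a tabulated split for capmatinib dosing, adverse events and laboratory shifts. Listings would let someone rebuild the split by hand, but no summary makes it.

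A reader might also infer that pooling flatters the combination. Step 3 shows that RDI can move either way, while crude event counts move against the combination if they move at all.

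A further objection is that a cut soon after the last infusion is not neutral. Protocol 4.5.2 warns that immune-related events may appear after treatment stops. Cutting dosing at + 27 days and adverse events at 150 days would place such an event in one period and the capmatinib hold it caused in the other. This is right, and it is why a single boundary is needed.

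**Conclusion.** The point holds in a limited form and is a cheap improvement. It covers capmatinib dose intensity and RDI, capmatinib reductions and interruptions, on-treatment adverse event summaries and laboratory shifts, in subjects who received spartalizumab. For these, no planned summary isolates the combination. The pooling itself follows directly from the SAP's definitions.

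Its size cannot be known from the documents, because capmatinib-alone durations and dosing levels are not given. The figures in steps 2 to 4 rest on assumed inputs and show only the possible range. Two inferences should be avoided. The 16 to 19 combination subjects still on capmatinib on 06-Sep-2021 are not the number who switched, since anyone who switched and stopped within those 40 days is missed. Nor do the documents show that monotherapy lasted years: there is no fixed end, but transfer out of the study is allowed once its conditions are met.

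**What to change.** In SAP 2.4.1.3, 2.4.2 and 2.8, for subjects who received at least one dose of spartalizumab, add summaries by period:

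- **Combination-attributable:** first dose to 150 days after the last spartalizumab dose, or to the end of the on-treatment period if earlier.
- **Capmatinib alone:** the remainder.

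Apply this one boundary to capmatinib dose intensity and RDI, reductions, interruptions, adverse events and laboratory shifts, so that a delayed immune-related event and the dose change it causes fall together. Repeat with last infusion + 27 days, already derived in SAP 2.4.1.1, as a sensitivity cut. Keep the pooled tables, and base statements about the combination's tolerability on the by-period tables.

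The cost is period flags from dates already collected and a few more tables, with shorter follow-up in the combination period. The main drawback is that the 150-day window still holds some capmatinib-alone time, up to 150 − 27 = 123 days per subject. For a subject with infusions on days 1, 29 and 57, spartalizumab exposure ends on day 84 and the window on day 207, so 123 of 207 days are capmatinib alone. The sensitivity cut should therefore be shown beside the main one, above all for RDI.

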#### 2.4.2 Dose reductions, interruptions and permanent discontinuations

The number of subjects who have dose reductions, permanent discontinuations or interruptions, and the reasons, will be summarized separately for each of the study treatment components.

The 'Type of change' field from the study treatment CRF pages will be used to determine the dose interruptions. Dose reductions will be derived programmatically using the dosing information as described below.

The corresponding fields 'Reason for change' will be used to summarize the reasons.

A dose change is recorded when 'Dose change' is entered on the 'Type of change' field on the DAR CRF page, where actual dose administered/total daily dose is different from the prescribed dose. In protocol version 01, dose re-escalation of capmatinib after dose reduction will be allowed only once, given no AE leading to dose modification is observed after at least 1 cycle (4 weeks) of study treatment at the reduced dose. The dose re-escalation will be considered as a dose change. For the purpose of summarizing interruptions and reasons, in case multiple entries for interruption that are entered on consecutive days with different reasons will be counted as separate interruptions. However, if the reason is the same in this mentioned multiple entries on consecutive days, then it will be counted as one interruption.

**Dose reduction** (only for capmatinib): A dose reduction where the prescribed dose level is lower than the previous prescribed dose level or where the actual dose administered/total daily dose is lower than the calculated dose amount based on the prescribed dose. Therefore, any dose change to correct a dosing error will not consider a dose reduction. Only dose change is collected in the CRF, number of reductions will be derived programmatically based on the change and the direction of the change.

**Dose interruption:** Actual dose administered equal to zero, between the first and last non-zero doses, following a non-zero actual dose administered. Number of dose interruptions and corresponding reason will be summarized.

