### **6.2.2.2 Spartalizumab: prohibited medication**

The use of systemic steroid therapy (at doses greater than 10 mg/day of prednisone or equivalent) and other immunosuppressive drugs is not allowed to subjects receiving spartalizumab, with the exception of:

- Topical, inhaled, nasal and ophthalmic steroids
- prophylactic use for subjects with imaging contrast dye allergy
- Replacement-dose steroids (defined as  $\leq 10$  mg/day of prednisone or equivalent dose of corticosteroids) in the setting of adrenal insufficiency.
- Transient exacerbations of other chronic inflammatory conditions, such as chronic obstructive pulmonary disease (COPD), requiring treatment. Steroids must be reduced to 10 mg/day (or lower dose) of prednisone or equivalent dose of corticosteroids prior to the next treatment with spartalizumab.
- Upon treatment of spartalizumab-related infusion reactions or spartalizumab-related irAEs, steroids must be reduced to  $\leq 10$  mg/day (or lower dose) of prednisone or equivalent dose of corticosteroids prior to the next treatment with spartalizumab. Systemic corticosteroids must be tapered, and be at non-immunosuppressive doses, prior to the next administration of study treatment. If the dose of prednisone or equivalent cannot be reduced to  $< 10$  mg/day before the administration of next dose of study treatment then spartalizumab/ placebo must be discontinued (note: next dose of spartalizumab/placebo can be delayed up to 12 weeks).

The use of live vaccines is not allowed from 4 weeks prior start of study treatment and up to 150 days from last dose of spartalizumab/placebo. Inactivated vaccines are allowed.

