### 12.5.2.3 Tolerability

Tolerability of study drug will be assessed by summarizing the number of and reasons for dose delays/interruptions and dose reductions. Dose intensity will also be tabulated by treatment group for each component of the study treatment.

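### SAP 2.4.2 gives two rules for dose interruptions without ranking them; one cannot count a spartalizumab hold still open at the sponsor stop, and delays promised in the protocol are left out

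*SAP*

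**What the plan says.** Protocol 12.5.2.3 says that tolerability will be assessed by "summarizing the number of and reasons for dose delays/interruptions and dose reductions", with dose intensity tabulated for each component. Spartalizumab is given once every 28 days. Protocol 6.5.1 does not permit its dose to be reduced but does permit interruptions for toxicity. Protocol 6.2.2.2 notes that the "next dose of spartalizumab/placebo can be delayed up to 12 weeks".

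SAP Table 1-1 gives the endpoint as "Tolerability: dose interruptions, reductions, and dose intensity". SAP 2.4.2 says that "dose reductions, permanent discontinuations or interruptions, and the reasons, will be summarized separately for each of the study treatment components". It contains two rules for interruptions:

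- "The 'Type of change' field from the study treatment CRF pages will be used to determine the dose interruptions"
- A dose interruption is "Actual dose administered equal to zero, between the first and last non-zero doses, following a non-zero actual dose administered".

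The second rule applies to both drugs. The SAP has no category for a delayed infusion, and its section 4 declares no change from the protocol's analyses.

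The Amendment 1 rationale records that, right after the enrollment halt of 28-Jul-2021, "All ongoing subjects were discontinued from spartalizumab treatment". The Study Update counts 28 patients treated with the combination by that date.

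**The concern.** The first-to-last-dose definition suits capmatinib, which is dosed continuously. It fits poorly with an infusion given every 28 days that was then stopped by the sponsor in everyone still receiving it. An infusion withheld for an adverse event at that moment has no later non-zero dose to close the window, so the definition excludes it whatever its cause. If the site then records the end of spartalizumab as a sponsor decision, the discontinuation table carries that reason and not the adverse event.

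An infusion that is held and then given late is a delay, which the protocol says it will summarize and the SAP does not mention. It counts as an interruption only if the CRF happens to produce a suitable entry.

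Tolerability is a secondary objective of Part 1, and lack of tolerability of the combination is the stated reason for the halt. With reductions ruled out for spartalizumab, holds and delays are the main direct record of dose modification short of permanent discontinuation.

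**Working it through.** **The SAP's own figures.** The worked examples in SAP 2.4.1.2 and 2.4.1.3 reproduce:

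- Capmatinib dose intensity: 40 000/56 = 714 mg/day; planned: 44 800/56 = 800 mg/day.
- Spartalizumab dose intensity: 28 × (800/56) = 400 mg/cycle.
- Expected infusions in 60 days: 60/28 = 2.14, rounded up to 3, as the SAP states.

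**Rules applied to spartalizumab**

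- Interruptions: zero-dose records strictly between the first and last non-zero doses (second rule of SAP 2.4.2).
- Exposure (SAP 2.4.1.1): last infusion day + 27 − first infusion day.
- Expected infusions: exposure/28, rounded up. This is my reading of the 60-day example.
- RDI: infusions given / expected infusions, because dose and duration cancel.

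**Hypothetical records, 400 mg per infusion**

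| Record | Interruptions | Exposure (days) | Expected infusions | RDI |
|---|---|---|---|---|
| Infusions on days 1 and 29; third due day 57, held, never given because of the stop | 0 | 29+27−1 = 55 | 2 | 2/2 = 100% |
| Same hold (0 mg on day 57), resumed day 85 | 1 | 85+27−1 = 111 | 4 | 3/4 = 75% |
| Second infusion 14 days late (day 43), only infusions recorded | 0 | 43+27−1 = 69 | 3 | 2/3 = 67% |
| Same delay, 0 mg entered on day 29 | 1 | 69 | 3 | 67% |
| Second infusion 12 weeks late (day 113), only infusions recorded | 0 | 113+27−1 = 139 | 5 | 2/5 = 40% |
| Second infusion 3 days late (day 32, within window) | 0 | 32+27−1 = 58 | 3 | 2/3 = 67% |

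The exposure formula for spartalizumab lacks the + 1 used for capmatinib, so two on-time infusions give 55 days and not the 56 in the SAP's example. Adding 1 changes no RDI in the table.

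**What this shows**

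1. The first two rows differ only in whether treatment resumed. An open hold leaves no trace in the interruption count or in RDI.
2. Whether a late infusion is counted depends on whether a zero-dose record exists. The dosing CRF page is not in the documents, so this cannot be settled from them.
3. RDI registers a delay but does not identify it. On this reading, an infusion 3 days late and within window gives the same 67% as one 14 days late.

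**Size.** One missed subject is 1/28 = 3.6 percentage points of those given the combination. On an assumed range, 3 would be 3/28 = 10.7 and 5 would be 5/28 = 17.9. If the denominator is all 31 treated patients (Protocol 4.1), one is 1/31 = 3.2 points.

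**The case against.** The strongest reply is that the section's other rule handles these cases. If the CRF field governs, no first-to-last-dose limit applies. Protocol 6.5.1 requires every interruption or change in administration to be recorded on the dosing eCRF, so a toxicity hold should have an entry and a reason. That stands as far as it goes, but the SAP does not say that this rule prevails over the definition that follows it. Two programmers could produce different tables.

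Other outputs also carry part of the information. SAP 2.8.1 plans tables of adverse events leading to dose reduction or interruption and to discontinuation, SAP 2.4.1 a listing of all doses with reasons for change, and SAP 2.4.1.3 RDI by component. These are real safeguards with limits. The adverse-event tables refer to study treatment, which the SAP defines as both drugs together, and specify no split by component, although Protocol Table 6-3 contains toxicities for which only spartalizumab is held. A listing does not replace the promised count with reasons, and RDI misses the open hold.

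It can also be said that SAP Table 1-1 matches Protocol Table 2-1, which does not list delays. That is correct; the mismatch is with Protocol 12.5.2.3, and SAP section 4 does not mention it.

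A reader might infer that late infusions can never be counted, that toxicity holds disappear from the report, or that spartalizumab intolerance is under-reported overall. The documents do not support any of these. A zero-dose record would be counted, delays lower RDI, and holds may appear in the outputs above. Nor do the documents say what reason sites recorded for a subject already on hold at the stop.

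**Conclusion.** The point holds in a limited form. SAP 2.4.2 has two unranked rules. Under the first-to-last-dose rule, a spartalizumab toxicity hold open at the sponsor stop is not an interruption, RDI does not reveal it, and its adverse-event reason may be lost. Separately, the delays promised in Protocol 12.5.2.3 are dropped without being declared, so late infusions are not reliably counted. The interruption count and its reasons may therefore be too low; the rest of the tolerability reporting is not shown to be wrong.

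The size cannot be derived. The Study Update has 19 patients on capmatinib on 06-Sep-2021, of whom at most 3 never had the combination, so at least 19 − 3 = 16 combination patients were still on treatment. That is not a count of those affected: some may have stopped spartalizumab earlier, and only those with an infusion withheld at the stop matter.

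The conclusion assumes that the first-to-last-dose definition is the one programmed. For the open hold the result follows from the wording alone. For late infusions it depends on the unseen CRF. The analysis is descriptive and Part 2 is cancelled, so the consequence is confined to the tolerability summary.

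**What to change.** In SAP 2.4.2:

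1. State which of the two interruption rules governs.
2. For spartalizumab, count a scheduled infusion that was withheld, with its recorded reason, even if no infusion follows.
3. Tabulate adverse-event-driven holds open at the sponsor stop separately from discontinuations by sponsor decision.
4. Summarize delays with reasons, a delay being an infusion given after its scheduled date plus the 3-day visit window. Say how the scheduled date is set after an earlier delay, so that one late infusion is not counted again at later visits.

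A simple cut-off of more than 31 days since the previous infusion should not be used. With a ±3-day window at each visit, one infusion 3 days early followed by one 3 days late are 28 + 3 + 3 = 34 days apart, and both are within window.

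If delays are not to be summarized, declare the omission in SAP section 4. The cost is SAP wording and one derivation from infusion dates and recorded reasons. No new data collection is proposed, but how far the reasons can be recovered depends on what the dosing CRF captured.
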